Research Protocol

Protocol Title:

Early Stability of Short Implants with Shallow Threads in the
Posterior Mandible: A Controlled Clinical Pilot Study.

Date: August - 19- 2025

Principal Investigator

[name]

Thesis Supervisor:

[name] [name]

(Associate Professor of Oral and Maxillofacial Surgery)

University of Science and Technology,

Yemen.

1. Background and Rationale

Patients with severely resorbed posterior mandibles face a significant challenge. While short implants (SHI, $\leq 8\text{mm}$) offer a less invasive alternative to complex bone augmentation, they are associated with a higher risk of early failure, often linked to compromised stability during the critical healing phase known as the "stability dip." This dip, a period of osteoclast-mediated resorption, creates micromotion that can disrupt osseointegration. The role of implant macrodesign, specifically shallow threads, and bone density in modulating this early stability trajectory remains unclear. This study aims to prospectively compare the early stability dynamics of short (7mm) versus standard (11mm) shallow-threaded implants to provide evidence for their use as a viable graft-less solution.

2. Study Objectives and Hypotheses

· Primary Objective:

To compare the early stability dynamics (primary stability, stability dip, and onset of secondary stability) of 7 mm short implants (SHI) versus 11 mm standard implants (SDI), both with an identical shallow-threaded macrodesign, in the non-augmented posterior mandible over 4 weeks.

· **Secondary Objective:**

To assess the effect of bone density (D2 vs. D3) on these stability parameters.

Hypotheses:

- H_01 : No significant difference in primary stability (ITV, ISQ-T0) exists between SHI and SDI.
- H_02 : No significant relationship exists between baseline ISQ and the stability dip magnitude/duration for either implant type.
- H_03 : Bone density has no differential effect on stability parameters between SHI and SDI.

3. Study Design

A prospective, controlled, non-randomized clinical pilot study employing $\geq 80\%$ split-mouth design where anatomically feasible. Implant allocation follows clinical necessity principles:

- Short Implant (SHI; 7 mm): Sites with 8–10 mm bone height above the inferior alveolar canal.

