- Standard Implant (SDI; 11 mm): Sites with >10 mm bone height. Randomization is precluded on ethical grounds, as placing an SHI in a site suitable for an SDI violates the standard of care.

4. Participant Selection

· Inclusion Criteria:

- Aged 18–65 years.
- Posterior mandibular partial edentulism requiring implant placement.
- Native bone height of 8–13 mm above the inferior alveolar canal.
- Bone width ≥ 5.5 mm.

- Bone density classified as D2 (850–1250 HU) or D3 (350–850 HU) via pre-operative CBCT.
- Plaque Index ≤ 1 .
- ASA physical status I or II.
- Provides written informed consent.

- **Exclusion Criteria:**
- Absolute surgical contraindications.
- Uncontrolled diabetes (HbA1c $> 7\%$) or immunosuppression.
- History of head/neck radiation or bisphosphonate therapy.
- Active periodontitis (PPD > 5 mm) or bone pathology.
- Smoking > 10 cigarettes/day.
- Parafunctional habits.
- Previous bone grafting at the intended implant site.

5. Sample Size

The sample will consist of Ten participants receiving 20 implants (10 SHI, 10 SDI). This is a pilot feasibility sample, determined by strict eligibility criteria and a post-hoc power analysis indicating 80% power to detect a clinically significant difference in ISQ dip ($\Delta\text{ISQ} \geq 5$) with an alpha of 0.05.

6. Materials and Methods

• **Implant System:**

A tiologic TWINFIT implants (DENTAURUM GmbH). Both SHI (7mm) and SDI (11mm) share an identical design:

- 4.2mm diameter
- 5-degree taper
- Shallow threads (0.35-0.45mm),
- Sandblasted, acid-etched (SLA) surface.

· Key Equipment:

- CBCT Machine (Vatech EZ-3D) for pre-surgical planning and bone density assessment.
- Surgical motor (W&H Implantmed) with a 20:1 reduction handpiece.
- Calibrated torque wrench.
- Resonance Frequency Analysis (RFA) device (Penguin RFA) with type 4 SmartPegs.

7. Study Procedures

· Pre-Operative Phase:

1. Screening against inclusion/exclusion criteria.
2. Clinical examination and plaque index recording.
3. CBCT scan with Hounsfield Unit (HU) calibration using a hydroxyapatite phantom to determine bone density (D2/D3).
4. Obtaining written informed consent.

· Surgical Protocol:

1. Premedication: Ibuprofen 400 mg.
2. Asepsis with povidone-iodine (perioral) and chlorhexidine (intraoral).
3. Local anesthesia (2% lidocaine with 1:80,000 epinephrine).
4. Crestal incision and full-thickness flap elevation.
5. Osteotomy performed with an under-preparation protocol.

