6. Implant placement with slow manual seating. Insertion Torque Value (ITV) is recorded during the final 90° rotation.
7. SmartPeg attachment and baseline Implant Stability Quotient (ISQ) measurement using RFA (T0).
8. Closure with sutures.

· Post-Operative Care:

- Analgesics (Diclofenac) and antibiotics (Amoxicillin/Clavulanate).
- Instructions for soft diet and chlorhexidine mouth rinses.

- **Follow-up and Stability Monitoring:**

- Participants will return for ISQ measurements at the end of weeks 1, 2, 3, and 4 (T1, T2, T3, T4).
- At each visit, quadruple RFA measurements (buccal, lingual, mesial, distal) will be taken, and the mean ISQ value calculated.

8. Outcome Measures

- **Primary Stability:**

- Insertion Torque Value (ITV) in Ncm.
- Baseline ISQ value (T0).

- **Stability Dip Characteristics:**

- Dip Magnitude (Δ ISQ-min): Difference between ISQ at T0 and the lowest ISQ value (ISQ-min) recorded between T1-T4.
- Time of Dip (T-min): The week (T1-T4) at which the lowest ISQ value occurred.

- **Secondary Stability Onset:** The first timepoint where ISQ values consistently increase by ≥ 2 units from the ISQ-min.
- **Effect Modifier:** Bone density (D2 vs. D3) as a primary covariate.

9. Data Management and Statistical Analysis

- **Data Collection:**

De-identified data will be recorded on standardized Case Report Forms (CRFs) and stored in a password-protected electronic database (Excel).

- **Statistical Analysis:**

Will be performed using SPSS Statistics (v28). Analysis will include:

- Descriptive statistics for all variables.
- Paired t-tests (for bilateral cases) and independent samples t-tests (for full dataset) to compare primary stability (H_01).
- Pearson/Spearman correlation to assess the relationship between baseline ISQ and dip magnitude (H_02).
- Linear Mixed Models (LMM) to analyze longitudinal ISQ trajectories.

- Two-Way ANOVA to test the interaction effect of Implant Type and Bone Density on dip magnitude (H_03).
- A p-value of <0.05 will be considered statistically significant, with Bonferroni correction for multiple comparisons.

10. Ethical Considerations

- **Approval:**

This study has been approved by the University of Science and Technology Institutional Review Board. (IRB Approval No: **1447/0062/UREC/UST**).

- **Informed Consent:**

Written informed consent will be obtained from all participants after a detailed explanation of the study procedures, potential risks, and benefits.

· Confidentiality:

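### The H02 test correlates baseline ISQ (T0) with a dip computed from T0, so error in T0 pushes r above zero and favours 'higher baseline, larger dip'

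*Protocol*

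**What the plan says.** - Section 2 states H02 as: "No significant relationship exists between baseline ISQ and the stability dip magnitude/duration for either implant type". It is a null of no relationship, posed for each implant type.
- Section 8 defines dip magnitude as: "Difference between ISQ at T0 and the lowest ISQ value (ISQ-min) recorded between T1-T4". T0 is thus a component of the outcome. The time of dip is defined separately as "The week (T1-T4) at which the lowest ISQ value occurred" and does not use T0.
- Section 9 assigns to H02: "Pearson/Spearman correlation to assess the relationship between baseline ISQ and dip magnitude (H_02". No null value other than zero is given, and no allowance is made for the shared T0. The mixed model in the same section is assigned to ISQ over time, not to H02.
- Section 9 on significance: "A p-value of <0.05 will be considered statistically significant, with Bonferroni correction for multiple comparisons".
- Section 7, under follow-up: "At each visit, quadruple RFA measurements (buccal, lingual, mesial, distal) will be taken, and the mean ISQ value calculated".
- Section 5: "The sample will consist of Ten participants receiving 20 implants (10 SHI, 10 SDI".

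**The concern.** Suppose an implant's T0 reads high by chance. Its baseline is then too high and its dip too large by the same amount; a low reading does the reverse. This alone produces a positive correlation. It is the familiar problem of correlating a change with its own starting value (mathematical coupling, regression to the mean).

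H02 is one of three stated hypotheses, and section 11 sends the results to a thesis and a journal. A significant positive r would be read as biology, namely that implants with higher initial stability lose more of it. The planned p-value cannot separate a real relationship from the arithmetic. The tilt also works the other way: a real inverse relationship can be cancelled and missed.

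**Working it through.** **The plan's own figure.** There is none for H02. The only power statement, 80% for a difference in dip of at least 5 ISQ (section 5), concerns another comparison and comes without an SD. Nothing in the protocol fixes the noise level, so the SDs below are assumptions.

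**Algebra.** Let b be true baseline, d true dip, and e independent visit-level error with SD se. Then T0 = b + e0. For one follow-up visit at the bottom of the dip, the observed dip is T0 − (b − d + e1) = d + e0 − e1. If H02 is true (d independent of b):

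- Cov(T0, dip) = Var(e0) = se², which is positive whenever there is any error.
- r = se² / √[(sb² + se²)(sd² + 2se²)], with sb the SD of b and sd the SD of d.

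With sb = 5 and sd = 3:

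- se = 1: 1/√(26 × 11) = 0.06
- se = 2: 4/√(29 × 17) = 0.18
- se = 3: 9/√(34 × 27) = 0.30

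**Simulation with the dip as the protocol defines it.** T1–T4 = b − d × (0.4, 0.8, 1.0, 0.6) + error, and dip = T0 − min(T1..T4). Settings: n = 10 (one implant type), sb = 5, mean d = 5, d independent of b, two-sided Pearson test at 5% (critical |r| = 0.632), 100,000 replicates per setting. H02 is true throughout.

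| Visit-level SD | Mean r, equal dips | False rejection, equal dips | Mean r, dip SD 3 | False rejection, dip SD 3 | Positive false rejections, dip SD 3 (nominal 2.5%) |
|---|---|---|---|---|---|
| 0 | – | – | 0.00 | 5.0% | – |
| 1 | 0.14 | 6.9% | 0.06 | 5.3% | 3.7% |
| 1.5 | 0.21 | 9.3% | 0.13 | 6.5% | 5.4% |
| 2 | 0.28 | 13.2% | 0.20 | 8.7% | 8.1% |
| 3 | 0.40 | 22.8% | 0.33 | 16.8% | 16.5% |

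The row with no error confirms that T0 error is the cause. The excess is almost entirely in the positive tail.

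**Sensitivity.**

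- *Averaging.* If independent reading error of SD 3 were the only source, a mean of four readings has SD 3/√4 = 1.5, giving 9.3% (equal dips) or 6.5% (dip SD 3). Visit-level SD 3 is therefore an upper end.
- *Spearman.* With dip SD 3, Spearman rejects 5.3%, 6.1%, 7.8% and 13.9% at visit-level SD 1, 1.5, 2 and 3. Ranking does not remove the problem.
- *A different dip profile.* With follow-up fractions 0.5, 0.9, 1.0, 0.6, mean dip 6 and dip SD 3, mean r is 0.06, 0.19 and 0.33 at se 1, 2 and 3, with rejection 5.3%, 8.4% and 16.2%. Pooling all 20 implants makes it worse: 5.4%, 13.6% and 31.7%.
- *Masking.* Under the same profile with se = 2, a true slope of −0.2 (dip falls 0.2 ISQ per ISQ of baseline) gives mean r of about −0.02, so the real inverse relation disappears.

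**The case against.** **Bonferroni.** The rates above use an uncorrected 5%, whereas the plan mentions Bonferroni. The family is not stated. At 0.05/2 with dip SD 3, rejection is 2.7%, 3.3%, 4.7% and 9.9% at visit-level SD 1, 1.5, 2 and 3; at 0.05/3 it is 1.8%, 2.2%, 3.3% and 7.3%. Most of these are below 5%. This stands as arithmetic but is not a remedy. The fair yardstick is the corrected level: 4.7% against 2.5% at SD 2 is still nearly double. The correction moves the threshold and leaves the centre of r where it was.

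**Size.** The magnitude rests on assumptions. Equal true dips are an extreme case, and at visit-level SD 1 to 1.5 with varying dips the inflation is slight. This stands, and the conclusion is conditional for that reason.

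**Averaging at T0.** The four-reading rule appears under follow-up visits; the surgical step in section 7 mentions only a baseline measurement. If T0 were a single reading with error SD 3 and the follow-ups were means of four (SD 1.5), false rejection would be 18% (dip SD 3) or 30% (equal dips). The ambiguity makes the bias larger, if anything.

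**A direct repair exists.** Correlating the dip with a separate T0 reading, whose error is independent of the T0 used in the dip, brings mean r back to 0.00 and rejection to 4.7–5.2% in simulation. That is correct for reading error. It does not remove error shared by all readings at the visit, and the protocol does not say that several readings are taken at T0. The mixed model could in principle separate error from baseline, but it is not assigned to H02 and 10 implants per type give it little to work with.

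**Consequence.** This is a pilot, and H02 drives no treatment or stopping decision. That limits the harm but does not make the test valid.

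**Conclusion.** The concern holds. Under H02, any error in T0 centres the planned correlation above zero, and the test against r=0 is tilted towards a positive finding. The mechanism and direction follow from the protocol's own definitions. The size does not: over visit-level SD 1 to 3, with between-implant SD 5 and n = 10, false rejection at nominal 5% runs from 5.3% to 16.8% with dip SD 3 and from 6.9% to 22.8% with equal dips. If visit-level noise is low the effect is negligible, and the protocol has no figure that settles this. The duration limb of H02 is not affected, because the time of dip is not computed from T0. The point should be fixed before analysis; it does not undermine the trial as a whole.

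**What to change.** In section 9, state that the p-value of the T0-versus-dip correlation against r=0 will not be used to reject H02. Report the correlation within each implant type as descriptive, with its confidence interval and a sentence saying that T0 is shared by both variables and biases r upwards. The interval is shifted in the same way, so whether it excludes 0 should not be read as a test.

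Two optional additions, each labelled with its limits:

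- *ITV versus dip magnitude, as exploratory.* ITV error should be independent of ISQ error. Assuming ITV correlates 0.6 with true baseline, this rejects 4.9–5.2% under H02. Power is poor: if true dip rises 0.3 ISQ per ISQ of baseline, 10%, 8% and 7% at visit-level SD 1, 2 and 3; for 0.5, 17%, 14% and 11% (dip SD 3). It answers a different question and must not replace H02.
- *Oldham's method at a fixed visit, as a sensitivity analysis only.* It is valid if true dips are equal across implants (4.9–5.0% at T3) and biased negative otherwise. With dip SD 3 it rejects 11.0%, 9.6%, 8.4% and 7.2% at visit-level SD 1, 1.5, 2 and 3, so it is worse than the raw test when noise is low.

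The cost is two or three sentences and no new data. The magnitude limb of H02 loses its confirmatory p-value, which is a small loss here. For r = 0.30 at n = 10, Fisher's z is 0.310 with standard error 1/√7 = 0.378, so the 95% interval already runs from −0.41 to 0.78.

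### H_03 is tested with calibrated HU cut at 850 into D2/D3 and with pairing ignored; a continuous-HU test would use the data better if the HU effect is roughly linear

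*Protocol*

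**What the plan says.** - Section 2 words H_03 as: "Bone density has no differential effect on stability parameters between SHI and SDI". The secondary objective in the same section is worded as a comparison of D2 with D3.
- Section 4 sets eligibility: "Bone density classified as D2 (850–1250 HU) or D3 (350–850 HU) via pre-operative CBCT". The value 850 belongs to both classes.
- Section 7 obtains the measurement: "CBCT scan with Hounsfield Unit (HU) calibration using a hydroxyapatite phantom to determine bone density (D2/D3".
- Section 8 names the effect modifier: "Bone density (D2 vs. D3) as a primary covariate".
- Section 9 tests H_03 by "Two-Way ANOVA to test the interaction effect of Implant Type and Bone Density on dip magnitude (H_03". A linear mixed model is listed there only for the longitudinal ISQ trajectories.
- Section 5 gives the sample: "Ten participants receiving 20 implants (10 SHI, 10 SDI". Its power statement, "indicating 80% power to detect a clinically significant difference in ISQ dip", concerns the dip (5 ISQ or more), "with an alpha of 0.05". It does not mention the interaction.
- Section 3 allocates implants by bone height and aims for at least 80% split-mouth cases. No quota, stratification or minimum count by density is stated.

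**The concern.** The protocol calibrates HU and then uses only which side of 850 a site falls on. Sites at 360 and 840 HU count as the same, and sites at 840 and 860 as different. An interaction is hard to estimate with 10 implants per type, and cutting the covariate makes it harder if dip magnitude changes gradually with density.

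Two further features weaken the test. The D2/D3 mix within each implant type is left to chance, so a cell may hold very few implants. If a cell is empty, the 2x2 interaction cannot be estimated. A plain two-way ANOVA also treats the 20 implants as independent, although most patients contribute one of each type.

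At stake is how much the trial can say about H_03 from data it already collects.

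**Working it through.** **1. The plan's own figure.** The 80% power is for a 5-ISQ difference between implant types, 10 per group, alpha 0.05. No SD is stated, so it can be neither reproduced nor refuted. Solving for the SD (two-sided, unpaired):

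- normal approximation: SD = 5 / [(1.960 + 0.842) × √(2/10)] = 5 / 1.253 = 3.99
- noncentral t, 18 df: SD = 3.77

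I use 3.77 to 3.78 below as the residual SD. This is an inference from the power statement, not a documented value.

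**2. Information kept by the cut, if the effect is linear.** For a normal covariate with share p above the cut, the fraction kept is φ(z_p)² / [p(1−p)]:

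- p = 0.5: 0.1592 / 0.25 = 0.64
- p = 0.3: 0.1209 / 0.21 = 0.58
- p = 0.2: 0.0784 / 0.16 = 0.49

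For assumed HU shapes restricted to 350–1250 and cut at 850, the squared correlation of HU with the D2 indicator is:

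- uniform: 74%
- normal centred at 850 (SD 150 or 200): 64% to 66%
- centred at 700 (SD 150 or 200): 46% to 56%
- centred at 650 (SD 150): 35%

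The loss is thus about 26% to 65%. A centre of 600 (SD 150) loses more (75%), but then only 5% of sites are D2. A distribution strongly bimodal around 850 would lose less.

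**3. Sparse cells.** Let p be the D2 share (not given in the protocol), with 10 implants per type.

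- Sites independent: P(at least one empty cell) = 1 − [1 − p¹⁰ − (1−p)¹⁰]²
- Both sites of a patient always in the same class: p¹⁰ + (1−p)¹⁰

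| D2 share | Empty cell, independent | Empty cell, shared class | Some cell with 0 or 1, independent | Some cell with 0 or 1, shared class |
|---|---|---|---|---|
| 50% | 0.4% | 0.2% | 4% | 2% |
| 30% | 5.6% | 2.8% | 28% | 15% |
| 20% | 20% | 11% | 61% | 38% |

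**4. Interaction power, continuous v cut, linear effect.** Simulation with 10 + 10 implants, HU normal with SD 200 truncated to 350–1250, residual SD 3.77, and slopes differing by 2 ISQ per 100 HU. Alpha is 0.05 without Bonferroni, and an empty cell counts as no detection.

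| Mean HU | Continuous | D2/D3 |
|---|---|---|
| 850 | about 45% | about 32% |
| 750 | about 45% | about 26% |
| 650 | about 41% | about 16% |

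Repeated runs agree within about 3 percentage points. A second set used a larger slope difference (5.5 ISQ per SD of HU, residual SD 3.78). It gave 78% v 58% for uniform HU and 74% v 24% for HU centred at 700 (SD 150). All these runs use independent errors, so they show the effect of the cut and not that of the pairing.

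**5. The same comparison if the effect is a step at 850.** Set-up as in step 4, mean HU 850. For an 8-ISQ step, power is about 35% continuous v 56% D2/D3. For a 5-ISQ step it is 18% v 26%. The ranking reverses.

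**6. How far the sample limits H_03 in any case.** The SE of the 2x2 interaction is SD × √(Σ 1/n), with 16 df. With SD 3.78 and cells 5/5/5/5, SE = 3.78 × √0.8 = 3.38. Power for a 5-ISQ difference of differences is 28%, and the interaction detectable with 80% power is 10.1 ISQ. With cells 2/8/2/8 these become 20% and 12.6 ISQ. With 1/9/1/9 they become 13% and 16.8 ISQ.

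**The case against.** The strongest reply is that D2 v D3 is the stated question: the secondary objective and the effect modifier are both worded that way, so the ANOVA matches them. This stands as far as it goes. There is no contradiction within the document, and a linear slope is a different estimand, so the class contrast should remain a reported result. It does not remove the loss, because H_03 itself speaks of bone density without classes.

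The gain also depends on linearity. With a step at 850 the cut is the better test, and a plot with 10 points per type is a weak check. This stands too. The protocol gives no reason to expect a step there, but it does not rule one out. A reader might infer that D2/D3 is the poorest form the variable could take; the documents do not support that, because the shape of the effect is unknown.

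A reader might also infer that a null H_03 would mainly reflect the cut. It would not. In step 4 continuous HU still misses the interaction in about 55% to 59% of runs, against about 68% to 84% with the cut. Most of the failure to detect comes from having 20 implants.

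Finally, empty cells are rare near an even split (0.4% or less), and this is a pilot with density as a secondary objective. Both are fair and limit the weight of the point. However, the protocol itself fixes the binary form and the test, so this is not merely detail left to an SAP.

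**Conclusion.** The point holds in a limited form. Section 9 tests H_03 on a cut version of a variable measured on a continuous scale, ignores the within-patient pairing, and leaves the D2/D3 counts per implant type uncontrolled. If the HU effect is roughly linear, the cut costs about a quarter to two thirds of the density information and, in the scenarios of step 4, about 13 to 25 percentage points of interaction power. Sparse cells matter only if one class is about 30% of sites or less.

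The HU distribution, D2 share, residual SD and slope are assumptions, so the direction under linearity is firm and the size is not. Continuous HU improves the test without making it adequate, so H_03 is exploratory under either analysis. This is a cheap improvement, held with medium confidence.

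**What to change.** In Section 9:

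- Test H_03 with a model of dip magnitude on implant type, centred continuous HU and their interaction, with a patient effect.
- Report fitted SHI and SDI values, with confidence intervals, at one representative D2 and one representative D3 HU chosen in advance.
- Keep the D2 v D3 by implant type contrast, also with a patient effect and with the four cell counts shown, as a supporting analysis for the secondary objective. State to which class a value of exactly 850 belongs.
- Label H_03 exploratory.

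The cost is a few lines of wording, with no new data or visits. The downside is that the continuous test assumes an approximately linear HU effect and would lose power to the D2/D3 contrast if the true effect were a step at 850. Reporting both lets readers see whether the conclusion depends on that assumption.

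### Bonferroni in Section 9 is valid, but Holm's step-down procedure on the same tests rejects at least as much at the same family-wise error

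*Protocol*

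**What the plan says.** The protocol's rule on multiplicity is the last item of the statistical analysis list in Section 9: "A p-value of <0.05 will be considered statistically significant, with Bonferroni correction for multiple comparisons". It does not list the tests in the corrected family or give their number.

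The tests named in the same section are:
- for H_01: "Paired t-tests (for bilateral cases) and independent samples t-tests (for full dataset) to compare primary stability (H_01"). Section 2 ties H_01 to two outcomes, insertion torque and baseline ISQ;
- for H_02: "Pearson/Spearman correlation to assess the relationship between baseline ISQ and dip magnitude (H_02");
- for H_03: "Two-Way ANOVA to test the interaction effect of Implant Type and Bone Density on dip magnitude (H_03");
- in addition, linear mixed models for the ISQ trajectories.

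Section 5 fixes the size of the study: "The sample will consist of Ten participants receiving 20 implants (10 SHI, 10 SDI"). It states "80% power to detect a clinically significant difference in ISQ dip ($\Delta\text{ISQ} \geq 5$) with an alpha of 0.05" and describes the sample this way: "This is a pilot feasibility sample, determined by strict eligibility criteria". Section 3 describes the pairing: "A prospective, controlled, non-randomized clinical pilot study employing $\geq 80\%$ split-mouth design where anatomically feasible".

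**The concern.** Plain Bonferroni holds every test in a family of m to 0.05/m, whatever the other tests show. Holm orders the same p-values and compares them in turn with 0.05/m, 0.05/(m−1), and so on up to 0.05, stopping at the first that fails. For accepting or rejecting hypotheses it is never worse than Bonferroni, and it carries the same error guarantee. A plan that names plain Bonferroni therefore gives up some power without gaining error control.

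What is at stake is the second and later real effects in the family. Some would be called non-significant under Bonferroni although Holm would reject them on the same data.

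**Working it through.** **Inputs.** From the protocol: alpha 0.05 with Bonferroni (Section 9); 10 participants, 10 short and 10 standard implants (Section 5); 80% power for a difference of 5 in ISQ dip at alpha 0.05 (Section 5); at least 80% split-mouth (Section 3). Assumed, because not given: the number of tests m (3 to 5), the number of real effects, the size of each effect, two-sided tests, and correlation between outcomes (0 or 0.5).

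**The plan's own 80%.** It cannot be reproduced, because no standard deviation is stated. Solving backwards with the noncentral t distribution, 80% power for a difference of 5 implies:
- independent t-test, 10 v 10: standardised difference 1.325, so SD = 5/1.325 ≈ 3.8;
- 10 pairs: standardised difference 0.996, so SD of the differences = 5/0.996 ≈ 5.0;
- 8 pairs: standardised difference 1.156, so SD of the differences = 5/1.156 ≈ 4.3.

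**Why Holm is at least as good.** Its first threshold, 0.05/m, is Bonferroni's, and every later one is larger. For m = 3 the thresholds are 0.0167, 0.025 and 0.05, against 0.0167 throughout. Every Bonferroni rejection is therefore also a Holm rejection. For the error rate, suppose m₀ of the m null hypotheses are true. When Holm first rejects a true null, at most m − m₀ hypotheses have been rejected before it, so the threshold in use is at most 0.05/m₀. The chance that any of the m₀ true nulls has a p-value that small is at most m₀ × 0.05/m₀ = 0.05. No assumption about dependence is used, and the tests may be t-tests, correlations or interaction tests.

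**Size of the gain, 10 pairs.** Each real effect has a standardised difference of 0.996 (80% power as a single test). Bonferroni power is the noncentral t power at 0.05/m; Holm power is simulated. Entries are power per real effect; ranges cover correlations of 0.5 and 0.

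| m | Bonferroni | Holm, one real | Holm, two real | Holm, all real |
|---|---|---|---|---|
| 3 | 60% | gain ≤ 0.3 points | about 65% | 71–72% |
| 4 | 54% | gain ≤ 0.3 points | about 58% | 67–68% |
| 5 | 50% | gain ≤ 0.3 points | about 52% | 63–64% |

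The differences are about 2 to 5 points with two real effects and 11 to 14 points with all real.

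**Same check with independent t-tests, 10 v 10, correlation 0.** For m = 3: 63.0% v 67.3% with two real effects (4.3 points) and 63.0% v 73.7% with all real (10.7 points). For m = 5: 54.3% v 56.4% (2.1 points) and 54.7% v 67.7% (13.0 points). The pattern is the same.

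**Chance of at least one true rejection.** Holm and Bonferroni differ by no more than 0.3 points in any setting, because both test the smallest p-value at 0.05/m.

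**Lower power.** With 10 pairs, all effects real and m = 3 to 5, the gain falls to about 2 to 5 points if single-test power is 40%, and to about 1 to 3 points if it is 30%.

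**Error rate.** The simulated family-wise error was about 5% or less for both methods, within simulation error.

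**The case against.** The strongest case against is that nothing here is wrong. Bonferroni is valid, conservative and stated in advance, no other passage conflicts with it, and the same remark could be made of any protocol that names it. That stands, and it limits the point to an optional improvement. A reader might infer that the multiplicity rule is an error; the protocol does not support that.

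The scenarios also go beyond the protocol. Section 9 assigns t-tests only to H_01; H_02 is a correlation and H_03 an interaction. The 80% in Section 5 concerns the dip alone and is carried over to every outcome by assumption. Ten complete pairs are not promised either; with 8 pairs the same standardised difference of 0.996 has 68% power, not 80%. This stands against the size of the gain, but not its direction, which holds for any set of valid p-values.

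Three stronger readings are tempting and should be resisted:
- That the cost is greatest because there are only ten participants. Holm's ordering holds at any sample size, and it helps only after a first rejection. If a small sample means low power, it helps less.
- That correlated outcomes make it worse. In the 80% scenario with all effects real and m = 3, Holm's power is slightly lower at correlation 0.5 than at 0 (71% v 72%).
- That Holm recovers the power lost to the correction. It recovers part of it, and only when more than one effect is real. Large figures for detecting every effect at once need every null hypothesis to be false with good power, which the protocol gives no reason to assume.

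Finally, the corrected family is not listed in Section 9. Holm does not settle that, but the gap does not defeat the change: whichever family is corrected, Holm rejects at least as much. A separate analysis plan may define it.

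**Conclusion.** The point holds as a minor, optional improvement. That Holm rejects everything Bonferroni rejects, at the same family-wise bound, is a mathematical fact and needs no assumption about this trial. The size is conditional. For 3 to 5 tests at 80% single-test power, it is near zero with one real effect, about 2 to 5 points per real effect with two, and about 11 to 14 points with all real; at 40% single-test power it is about 2 to 5 points with all real. These figures rest on an assumed number of tests, assumed effect sizes and 10 complete pairs. Nor would Holm cure a non-significant result from ten participants being read as no difference; reporting the interval estimate guards against that.

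**What to change.** In Section 9, replace the Bonferroni correction with the Holm step-down (sequential Bonferroni) correction, applied to whichever family of tests the investigators correct. Report each estimate with its unadjusted 95% confidence interval beside the Holm-adjusted p-value.

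The cost is one phrase in the protocol and sorting the p-values, which a spreadsheet can do. No data are added and the error bound is unchanged. The one real drawback is that Holm has no equally simple simultaneous confidence intervals. Where simultaneous intervals are wanted, Bonferroni intervals can still be shown, labelled as such. They may then include zero for a hypothesis that Holm rejects, and a sentence in the methods should say so.
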